19.2. Secondary Objectives

19.2.1. Secondary Objective # 1

Objective - Implant procedure related information: success rate, implant related times

The Attain Stability Quad LV lead implant success rate will be estimated as the number of subjects with Attain Stability Quad MRI SureScan LV Lead (Model 4798) successfully implanted divided by the total number of subjects who had a Attain Stability Quad MRI SureScan LV Lead (Model 4798) implant attempt. A 2-sided 95% Confidence Interval will be calculated using the Exact Binomial method.

The distribution of implant related times will be summarized through statistical summaries such as mean, standard deviation, minimum, median and maximum. Only subjects with the Attain Stability Quad MRI SureScan LV Lead (Model 4798) successfully implanted will be included in this calculation. The total implant time is defined as time from initial incision to final skin closure. Fluoroscopy time is defined as the total time the fluoroscope is imaging. Cannulation time is defined as the time from insertion of the first CS cannulation catheter to the first successful CS cannulation. Successful lead placement time is defined as the time from lead insertion of the successfully placed lead to the time when the lead is placed in its first acceptable pacing location.

19.2.2. Secondary Objective # 2

Objective - 6-month reliability: post implant lead failure modes

The Attain Stability Quad MRI SureScan LV Lead (Model 4798) is a composite of two existing market released Medtronic products. The helix fixation is identical to the Attain Stability LV Lead Model 20066/4796 (market released outside of the US). The remainder of the lead is similar to the Attain Performa LV Lead Model 4298, released worldwide.

Historical datasets will be used as informative priors for lead related complications. More specifically, analysis of all complications related to fixation (helix performance) will use data from the Attain Stability (Model 20066/4796) research study, conducted outside of the US. Analysis of all other lead related complications will use data from the Attain Performa clinical study, conducted globally. Credible intervals will be constructed for each individual failure mode within the two groups.

Historical Data (for secondary endpoints only)

- Fixation-related LV lead complications - Data from the 37 patients who completed 6-month follow up with a successfully implanted 20066 lead in the Attain Stability study will be used as an informative prior.
- All other LV lead-related complications - Data from the 401 patients who completed 6-month follow up in the Attain Performa 4298 study will be used as an informative prior.

These historical datasets will be downweighted such that their effective sample size will not exceed the 9% of the total sample size (i.e at most 37 subjects at 6 months).

Statistical Analysis Methods

The weighted historical data will be incorporated using the power prior method²⁴. The weight of the historical data will be adjusted using a loss function²⁵, which scales from 0 to 1 according to the similarity of the historical and observed data. This loss function adjusts the amount of weight the prior receives. The comparison between historical and observed data will be performed twice, once for each group of complications (fixation-related and all other). The objective of using a loss function with the power prior method is to reduce the influence of an informative prior in the parameter estimation, when the historical data does not agree with the current study data.

If analysis of failure rate shows a high level of agreement between historical and current study data or there is better performance for Attain Stability Quad MRI SureScan LV Lead (Model 4798) compared to historical data, the historical data will be weighted at or near a maximum level (9% of total effective sample size). If the Attain Stability Quad MRI SureScan LV Lead (Model 4798) performs worse than historical data, the historical data will receive very little or zero weight. Note that there will be two loss function weights, one for fixation-related complications and one for all other complications. Credible interval calculations will be done separately for individual failure modes within the two groups of complications (fixation and all other).

Denote by θ_c and θ_h the probabilities of lead complication for the current and historical studies respectively. The posterior distributions of θ_c and θ_h respectively, both with minimally informative priors are:

$$\begin{aligned}\theta_c &= \text{beta}(y_c + 1, n_c - y_c + 1) \\ \theta_h &= \text{beta}(y_h + 1, n_h - y_h + 1)\end{aligned}$$

These posterior distributions are then stochastically compared using a posterior Bayesian p-value²⁶ as:

$$p = P(\theta_c \leq \theta_h)$$

The desired characteristics for the loss function are:

1. For $p \geq \sim 0.5$, there is a high level of agreement between current and historical data, therefore the loss function should allow a_0 to be close to 1, allowing for full weight of historical data.
2. Conversely, for $p < \sim 0.5$, there begins to be evidence of disagreement between current and historical data, and a_0 should start to down-weight the prior, i.e. a_0 approaches zero as p approaches zero.

The Weibull cumulative distribution function (CDF) meets these criteria:

$$a_0 = 1 - e^{-(p*5)^2}$$

Note that for the case where the number of samples in the prior is different than the effective number, a scaling factor will be applied, where n_h is the desired effective number of prior samples and N_h is the actual number of prior samples:

[figure not shown]
$$a_0 = \frac{n_h}{N_h} [1 - e^{-(p*5)^2}]$$

Sample values are listed in Table 17 below and illustrated in Figure 7. The comparison between current and historical data will be performed for all LV lead fixation related complications using Attain Stability (Model 20066) historical data and for all other LV lead related complications using Attain Performa historical data.

Table 17: Prior weight from Attain Stability (Model 20066) and prior weight from Attain Performa as a function of the posterior Bayesian p-value (p)

	Prior weight from Attain Stability (Model 20066)	Prior weight from Attain Performa
p	$a_0 = 1 - e^{-(p*5)^2}$	$a_0 = \frac{37}{401} [1 - e^{-(p*5)^2}]$
0.01	0.002	0.000
0.05	0.061	0.006
0.1	0.221	0.020
0.2	0.632	0.058
0.5	0.998	0.092

Figure 7: Loss Function $a_0 = 1 - e^{-(p*5)^2}$

[figure not shown]

Note that the loss function proposed here does not reduce the strength of the prior when the current study outperforms the historical data. This implementation of the loss function is only concerned with negative impacts to patients, i.e. it penalizes an optimistic prior while not penalizing a pessimistic prior.

Also, note that this function is selected for the shape of the CDF rather than due to conventional statistical properties of the Weibull distribution.

Figure 8 illustrates the effect of the power prior coupled with the loss function. The figure shows credible intervals in scenarios where the prior is optimistic (better performance than current study), in agreement (similar performance to the current study), and pessimistic (worse performance than the clinical study). Note that the prior data source in Figure 8 is the Attain Performa study, with 401 patients. As will be discussed later, these data are scaled to represent a maximum of 37 patients (i.e. 9% weight).

Figure 8: Credible Intervals for Scenarios of Agreement Between Historical and Current Data

The prior data set in Figure 8 has 401 samples. However, the maximum effective historical data sample size is $n_h = 37$, for a maximum weight of 9%. Therefore, the prior will be scaled by a factor of $(37/401)$. As an example, illustrated in the middle panel above, if the effective sample size is 34 out of 37, the prior has received 89% of the maximum weight, or 8.5%.

The panels in Figure 8 can be interpreted as follows:

- **Top panel:** The current data shows lower performance than the prior. The loss function produces a substantial penalty resulting in almost no weight to the prior (1%). The posterior (final estimate) is essentially the same as the current study.
- **Middle panel:** The current data is very similar to the prior. The loss function penalty is small, resulting in a prior weight of 8.5% (recall that the maximum weight is 9.2%). Because the agreement is good, the posterior (final estimate) is similar to both the prior and current study.
- **Bottom panel:** The current data is very similar, with slightly better performance than the prior. The loss function produces a weight very close to the maximum of 9.2%. The posterior (final estimate) is a balance between the prior and current study.

Sample Size

A Bayesian adaptive design is set up to enroll patients until a sufficient sample size is achieved to have high probability of meeting the required effective sample size of $n_e = 400$. The number of enrolled patients in the study may vary from 363 to 400 subjects due to the adaptations to the trial. This study follows methods from Berry, et.al.²⁷

The interim analysis will take place after 360 subjects have been enrolled into the study.

The Adaptive Bayesian sample size algorithm will stop or continue enrollment accordingly to the following:

- 1.) If the predictive probability of $n_e \geq 400$ is larger than 80% then enrollment will stop.
- 2.) If the predictive probability of $n_e \geq 400$ is less than 80%, enroll sufficient additional patients to make the probability of $n_e \geq 400$ at least 80%.

At the time of the interim analysis, some patients will not have completed the full evaluation period. A longitudinal model will be employed to enable final observations to be imputed for those subjects with incomplete information.

There are 3 types of subjects at a given interim analysis:

- 1.) Subjects that have complete data
- 2.) Subjects that have partial data (censored value at a particular time)
- 3.) Subjects that have no information (subjects that have not been enrolled)

Predictive probabilities for types 2 and 3 will have to be computed. The predictive probability model that will be used is a piecewise exponential. This will allow the final outcomes for the subjects who have not had an event and have not completed 6 month follow up to be simulated.

Note this Bayesian approach to borrow information from historical datasets will only be used for the secondary objective #2.

19.2.3. Secondary Objective # 3

Objective – Electrical measurements (PCT and Impedance) at follow-ups

Pacing Capture Threshold (PCT) and impedance data will be collected using VectorExpress™. Pacing vector changes will be monitored for all implanted patients at follow-up visits.

Summary statistics for PCT and impedance at each time point (i.e. Implant, 6 months, etc.). The distribution of the electrical measurements at the final programmed pacing vector will be presented as n, mean, standard deviation, minimum, median and maximum. In the event of a replacement of a Medtronic Quad CRT-P or CRT-D device and/or the implanted LV lead, only measurements from the

Attain Stability Quad MRI SureScan LV Lead (Model 4798) implanted at the initial implant procedure will be included in the analysis cohort for this objective.

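### For the 37-patient fixation prior, the borrowing rule does not give the very small weight that Section 19.2.2 promises for a worse-performing lead, and a single group weight can mask one worse failure mode

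*Protocol*

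**What the plan says.** Protocol Section 19.2.2 borrows historical data for lead-related complications through a power prior. Two sources are used:

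- Fixation-related complications: "Data from the 37 patients who completed 6-month follow up with a successfully implanted 20066 lead in the Attain Stability study".
- All other LV lead complications: "Data from the 401 patients who completed 6-month follow up in the Attain Performa 4298 study".

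The borrowed amount is capped: "effective sample size will not exceed the 9% of the total sample size (i.e at most 37 subjects at 6 months". The cap scales the 401-patient prior by 37/401. The 37-patient prior is already at the cap and is not scaled.

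The weight comes from p = P(theta_c <= theta_h), where theta_c and theta_h are the current and historical complication probabilities, each with a Beta(y + 1, n - y + 1) posterior. The weight is a0 = 1 - exp(-(5p)^2), and Table 17 tabulates it. In words, the section says that if the new lead "performs worse than historical data, the historical data will receive very little or zero weight".

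One weight is set for the fixation group and one for the rest, but results are reported at a finer level: "Credible interval calculations will be done separately for individual failure modes within the two groups of complications". Figure 8, the only illustration of the discount, uses the 401-patient prior. Section 11.1.2 describes the secondary objectives as descriptive, with no performance requirement.

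**The concern.** The sentence tells a reader that the historical data all but vanish from the estimate once the new lead does worse. With only 37 historical patients the historical posterior is wide, so p stays well above zero even when the observed current rate is several points higher. The formula then keeps a substantial share of the prior.

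The second issue is the level at which agreement is judged. The weight is set on the group total and then used for each mode inside it. If one mode is worse than history and another is better, the group can look unchanged and the worse mode is combined with history at nearly full weight.

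What is at stake is how the fixation and mode-specific intervals are read. Someone relying on the sentence would take a borrowed interval for a worse-looking rate to be essentially current-study data.

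**Working it through.** **Inputs.** From Section 19.2.2: historical sizes 37 and 401; cap 37; Beta(y + 1, n - y + 1) posteriors; p = P(theta_c <= theta_h); a0 = 1 - exp(-(5p)^2), multiplied by 37/401 for the larger prior. The same section gives 363 to 400 current subjects; 400 is used here. The number of historical fixation events is not stated, so 0/37 and 1/37 are assumed. The splits by failure mode in step 4 are also assumed.

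**Step 1: the plan's own table.** The formula reproduces all ten entries of Table 17. For the fixation prior:

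| p | probability the new lead is worse (1 - p) | a0 |
|---|---|---|
| 0.01 | 99% | 0.002 |
| 0.05 | 95% | 0.061 |
| 0.1 | 90% | 0.221 |
| 0.2 | 80% | 0.632 |
| 0.5 | 50% | 0.998 |

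For example, 1 - exp(-(5 x 0.2)^2) = 1 - exp(-1) = 0.632. The rows at p = 0.1 and 0.2 already disagree with the sentence, whatever the historical event count.

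**Step 2: observed rates that lead to such p values.** p was obtained by numerical integration over the two Beta posteriors (a simulation check for 16/400 against 0/37 gave 0.208 both ways). Borrowed patients = 37 x a0.

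| Current | History (assumed) | p | a0 | Borrowed of 37 |
|---|---|---|---|---|
| 12/400 (3%) | 0/37 | 0.303 | 0.90 | 33.3 |
| 16/400 (4%) | 0/37 | 0.208 | 0.66 | 24.5 |
| 20/400 (5%) | 0/37 | 0.143 | 0.40 | 14.7 |
| 29/400 (7.25%) | 0/37 | 0.060 | 0.09 | 3.2 |
| 32/400 (8%) | 1/37 (2.7%) | 0.183 | 0.57 | 20.9 |

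With 0/37, 29/400 is the first count at which the weight is below 0.10. With 1/37 it is 46/400 (11.5%). With 363 current subjects the results are close: 15/363 against 0/37 gives 0.62, and 29/363 against 1/37 gives 0.57.

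**Step 3: the same kind of contrast with the larger prior.** 16/400 against 4/401 (4% against 1.0%) gives p = 0.003 and about zero weight. 32/400 against 11/401 (8% against 2.7%) gives p = 0.0004 and about zero weight. So the sentence is a fair description of the 401-patient prior, which is the one Figure 8 shows, and not of the 37-patient prior.

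**Step 4: group weight on one mode.** Suppose the non-fixation group is 16/400 against 16/401. Then p = 0.497 and the group gets 0.998 of the maximum weight, or 36.9 patients. Suppose one mode inside it is 12/400 against 4/401. Judged alone, p = 0.023 and it would get 0.013 of the maximum, or 0.5 patients. Under the plan it is combined with history at 0.998.

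**Step 5: effect on an interval.** The borrowed posterior is Beta(1 + y_c + a0 y_h, 1 + n_c - y_c + a0 (n_h - y_h)).

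- 12/400 against 0/37, no borrowing: Beta(13, 389), mean 3.2%, 95% interval 1.7% to 5.2%.
- With a0 = 0.899: 389 + 33.3 = 422.3, so Beta(13, 422.3), mean 3.0%, 95% interval 1.6% to 4.8%.
- 16/400 against 0/37: mean 4.2% (2.5% to 6.4%) without borrowing, 4.0% (2.3% to 6.0%) with it.

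**The case against.** The strongest reply is that the rule does what its formal specification asks. Section 19.2.2 wants down-weighting to begin below p of about 0.5 and the weight to approach zero as p does, and the formula meets both conditions. With 37 historical patients these contrasts are weak evidence of a difference: two-sided Fisher tests give 0.61 for 12/400 against 0/37, 0.38 for 16/400 against 0/37, and 0.34 for 32/400 against 1/37. A similarity-based discount should not collapse when the data cannot show dissimilarity. The formula and Table 17 are printed, group-level weighting is openly chosen, and the objective is descriptive.

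Most of this stands, and it rules out several stronger readings:

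- A reader might infer that a clearly worse lead still borrows most of the prior. The documents do not support that. The worse rates above are observed rates, not established differences, the historical count is assumed, and at p = 0.05 the weight is only 0.061. Even at 5% against 0/37 it is 0.40.
- A reader might infer that fixation borrowing would end enrolment early. The protocol does not say how the two group weights combine into the effective sample size of 400, so this cannot be shown.
- A reader might treat the helix as the lead's only new mechanical feature. Section 13.1 says it is identical to that of Model 20066/4796, and that body diameter and shape also differ from Model 4298.

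What the reply does not rescue is the sentence itself. It attaches very little or zero weight to worse performance without requiring strong evidence, and the table in the same section shows otherwise.

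**Conclusion.** The point holds as a mismatch between a stated property and the rule that is meant to provide it. The conflict with Table 17 needs no assumption. The rate examples (0.66 at 4% against 0/37, 0.57 at 8% against 1/37) depend on the assumed historical event counts and on 400 current subjects. The failure-mode example depends on an assumed offsetting split within the group.

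The size is modest. At most 37 patients are borrowed per group, and the upper limits computed here move by about 0.4 percentage points. The primary safety and efficacy analyses do not borrow. This does not show that the method is broken or that borrowing must be dropped. It shows that the discount is weaker for the fixation group than the text says, and that a reader of a borrowed mode-level interval cannot tell how much of it is history.

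**What to change.** 1. In Section 19.2.2, replace the sentence promising very little or zero weight with the weights the rule gives for 37 historical patients at stated event counts. State the historical fixation count and tabulate a0 over a range of current rates.
2. For every failure mode in both groups, report the credible interval without borrowing (a0 = 0) beside the borrowed one, with the a0 used and the number of borrowed patients.

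Per-mode weights, or making the no-borrowing result the main one for fixation, are possible but are trade-offs against an openly stated design and are not needed to correct this point.

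The cost is a few more table columns and a less favourable description of the discount. The planned enrolment and the primary analyses are unaffected.

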19.3. Additional Analysis

19.3.1. Poolability Analysis

Additional analysis will be conducted to summarize study primary objectives by patient characteristics, such as gender, age group, race and study site geography. The purpose of the poolability analysis is to identify if there is any clinical meaningful difference in a subgroup of patients. These analyses will not be statistically powered, and there is no pre-specified statistical significance level for these analyses.

19.3.2. Sensitivity Analysis

All subjects enrolled into this study and successfully implanted with a Medtronic Quad CRT-P or CRT-D device and Attain Stability Quad MRI SureScan LV Lead (Model 4798) will be included in the primary efficacy analysis datasets (efficacy objectives #1 and #2). Sensitivity analysis such as the Tipping Point method or similar will be conducted to investigate the influence of subjects who were successfully implanted with the required system however missed a 6 month post implant follow-up test(s) (due to reasons such as missing in-office visit, subject exit, death and/or the initial implanted lead was deactivated). For this purpose, all subjects with successful implant who do not meet analysis cohort requirements, will be considered as the worst case scenario (i.e. failure to meet the efficacy endpoints). The results will be submitted as part of the clinical reports.

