19.1.2. Primary Efficacy Objective #1**Objective**

The Attain Stability Quad MRI SureScan LV Lead (Model 4798) will meet the first primary efficacy objective if the proportion of subjects with at least one Attain Stability Quad MRI SureScan LV Lead (Model 4798) pacing vector having a pacing capture threshold (PCT) less than or equal to 2.5 V at 0.5ms pulse width at 6 months post-implant is greater than 80% (i.e., the lower bound of the one-sided 97.5% confidence interval must be greater than 80%).

Hypothesis

$H_0: P_{1_{6\text{-month}}} \leq 80\%$

$H_A: P_{1_{6\text{-month}}} > 80\%$,

[figure not shown]
where $P_{1_{6\text{-month}}}$ is the proportion of subjects with pacing voltage thresholds $\leq 2.5\text{V}$ at 0.5ms at 6 months follow-up visit post-implant for at least one LV lead pacing vector.

Endpoint Justification

The Attain Stability Quad MRI SureScan LV Lead (Model 4798) is equipped with the identical four electrodes to the Attain Performa LV leads. At the same time, the unique fixation mechanism may cause the distal end of the lead (tip) to be implanted away from the apical region of the heart, and therefore

the PCT may be slightly higher than the values observed in other Quadripolar LV leads. Therefore, we simulated the lead pacing threshold values based on the Attain Performa IDE study data, but excluding the PCT values collected at the most distal electrode. The simulation estimated that 89% of the subjects will achieve this endpoint (Figure 6).

Figure 6: Simulated PCT Distribution

Statistical Analysis Methods

All subjects with valid pacing thresholds measured at the 6 month follow-up visit will be included in this analysis. The proportion of subjects having at least one LV lead pacing vector with voltage thresholds less than or equal to 2.5V will be calculated. The lower bound of the 1-sided 97.5% Confidence Interval will be calculated using the Exact binomial method. Any subject in which no valid pacing threshold value is measured or who has an unable-to-capture result via all LV lead pacing vectors will be reviewed and adjudicated for a possible lead related AE but will not be included for this evaluation if the occurrence is deemed to be a system related event (e.g. lead dislodgement). However, this event may be counted against the safety primary endpoint based on the CEC's final classification.

Sample Size

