The primary efficacy endpoint will be analyzed using the Exact binomial method. In order to preserve the overall study power, a type II error less than 10% was used for the sample size calculation. A sample size of 145 subjects achieves 91% power to detect a difference of 0.1 using a one-sided binomial test at a target significance level of 0.025. These results assume that the population proportion under the null hypothesis is 80%, with an expected proportion of 90%.

Determination of Patients / Data for Analysis

All subjects enrolled into this study satisfying the following conditions will be included in this analysis:

- Successfully implanted with a Medtronic Quad CRT-P or CRT-D device and Attain Stability Quad MRI SureScan LV Lead (Model 4798)
- Completed 6-month follow-up visit
- Initially implanted Attain Stability Quad MRI SureScan LV Lead (Model 4798) is active at the 6-month follow-up visit
- At least one available and valid pacing threshold at the 6-month follow-up visit

19.1.3. Primary Efficacy Objective # 2

Objective

The Attain Stability Quad lead will meet the second primary efficacy objective if the proportion of subjects with at least one additional (or second) LV lead pacing vector having a pacing capture threshold less than or equal to 4.0 V at 0.5ms pulse width at 6 months post-implant is greater than 80% (i.e., the one-sided 97.5% lower confidence bound must be greater than 80%).

Hypothesis

$$H_0: P_{2_{6\text{-month}}} \leq 80\%$$

$$H_A: P_{2_{6\text{-month}}} > 80\%$$

where $P_{2_{6\text{-month}}}$ is the proportion of subjects with at least one additional LV lead pacing vector with pacing voltage thresholds $\leq 4.0V$ at 0.5ms at 6 months post-implant follow-up visit.

Endpoint Justification

The Attain Stability Quad MRI SureScan LV Lead (Model 4798) has 16 LV programmable pacing vectors . Subjects may have the pacing configuration programmed or reprogrammed at each clinic visit. A pacing threshold of 4.0 V will allow an adequate safety margin for programming LV pacing output. The maximum pacing amplitude of the CRT-P or CRT-D devices capable of programming pacing output to any LV lead pacing vector is 8.0V. In actual clinical practice, a less than 3V safety margin is used for the programmed LV lead pacing output in 99% of the patients.

Statistical Analysis Methods

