19.3.3. Overall Study Sample Size Requirements

The sample size requirement at 6-months for each of the study objectives is displayed in Table 18. The first row does not account for attrition, while the second row is inflated by 15% attrition. The sample size for Secondary Objective #2 assumes the conservative case that the interim look results in, no borrowing of historical data. Therefore, the overall sample size for the study is 471.

Table 18: Required Sample Size by Study Objective

	Primary Safety Objective	Primary Efficacy Objective #1	Primary Efficacy Objective #2	Secondary Objective #1	Secondary Objective #2 (post-implant failure modes)	Secondary Objective #3	Overall
Number needed at 6-months	170	145	50	NA	400	NA	400
Number of enrollments	200	171	59	NA	471	NA	471

20. Ethics

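### The efficacy sensitivity analysis names a tipping-point method but scores every non-evaluable implanted subject as a failure, so for objective #1 its result depends largely on how much attrition follows implant

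*Protocol*

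**What the plan says.** The primary efficacy analyses (Sections 19.1.2 and 19.1.3) use evaluable subjects only: successful implant, 6-month visit completed, initial lead still active, and "At least one available and valid pacing threshold at the 6-month follow-up visit". Each objective is met if the exact one-sided 97.5% lower bound exceeds 80%, and both must be met.

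Section 19.3.2 is the protocol's only provision for implanted subjects outside that cohort. It first says "Sensitivity analysis such as the Tipping Point method or similar will be conducted". The reasons it lists for a missing test are "due to reasons such as missing in-office visit, subject exit, death and/or the initial implanted lead was deactivated". It then sets the rule: "all subjects with successful implant who do not meet analysis cohort requirements, will be considered as the worst case scenario", which it explains as failing the efficacy endpoints. The results go into the clinical reports, and no pass criterion is attached.

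On attrition, Table 18 gives the numbers needed at 6 months in its first row, "while the second row is inflated by 15% attrition". The overall figures are 400 and 471. Section 12 speaks of up to 471 enrolled and up to 471 leads implanted, to secure 400 with a 6-month visit.

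**The concern.** A tipping-point analysis asks how badly the missing subjects would have to do before the conclusion changes. It varies their assumed success rate and reports where the result flips. The rule in Section 19.3.2 holds that rate at 0% for everyone. Once it is fixed, the result is roughly the evaluable success rate multiplied by the share of implanted subjects who are evaluable. For an objective expected to succeed in about 90% of subjects against an 80% bar, modest missingness is enough to push the result below the bar.

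Pooling the reasons makes this worse. A deactivated lead says something about the lead; a missed visit usually does not. A single all-failure figure cannot separate the two, so a reader of the report could not tell whether a result under 80% reflects the lead or the follow-up.

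**Working it through.** **Inputs (Protocol).** Bar 80%, exact binomial, one-sided 97.5% lower bound (19.1.2, 19.1.3). Objective #1: expected 90% for sample size; in addition, "The simulation estimated that 89% of the subjects will achieve this endpoint" (19.1.2). Objective #2: expected 97%, with 97.7% observed for the predecessor lead (19.1.3). Attrition 15%; 400 evaluable, 471 enrolled (Table 18).

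**The plan's own figures reproduce.** The plan states: "A sample size of 145 subjects achieves 91% power to detect a difference of 0.1 using a one-sided binomial test". With n = 145, the smallest passing count is 126, with type I error 0.0204 and power 0.913. With n = 50, the count is 46 and power 0.983, against a stated 98%. Attrition: 145/0.85 = 171, 50/0.85 = 59, 400/0.85 = 471.

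**Formula for the Section 19.3.2 rule.** With N implanted, 400 evaluable and x evaluable successes, the estimate is x/N. The lower bound L is the 2.5th percentile of Beta(x, N − x + 1).

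**All attrition after implant (N = 471, 71 missing).**

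| Objective, evaluable success | x/N | Estimate | Lower bound |
|---|---|---|---|
| #1, 90% | 360/471 | 76.4% | 72.3% |
| #1, 89% | 356/471 | 75.6% | 71.4% |
| #2, 97% | 388/471 | 82.4% | 78.6% |
| #2, 97.7% | 391/471 | 83.0% | 79.3% |

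For #1 the point estimate is itself below 80%. For #2 only the bound falls short. The bound first exceeds 80% at 395 successes (394/471 gives 79.997%, 395/471 gives 80.2%), so 395/400 = 98.75% of evaluable subjects would have to succeed.

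**Some attrition before implant.** The protocol gives no split, so the splits below are assumptions, each with 400 evaluable. N is 471 less the never-implanted subjects.

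| Points of the 15 never implanted | N | Missing among implanted | #1 at 90%, bound | #2 at 97%, bound |
|---|---|---|---|---|
| 0 | 471 | 71 | 72.3% | 78.6% |
| 3 | 457 | 57 | 74.7% | 81.3% |
| 5 | 447 | 47 | 76.6% | 83.3% |
| 8 | 433 | 33 | 79.3% | 86.3% |
| 10 | 424 | 24 | 81.1% | 88.4% |

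Break-even for #1 at 90% is N = 429 (360/429, bound 80.1%): 42 of 471 never implanted, or 8.9 points. At 89% it is N = 424 (356/424, bound 80.1%): 47 of 471, or 10.0 points. For #2 at 97% it is N = 463 (388/463, bound 80.1%): 8 of 471, or 1.7 points.

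**What a tipping-point analysis would report (N = 471, 71 missing, 395 successes needed).**
- #1 at 90%: 395 − 360 = 35 of 71 (49%) must be successes.
- #1 at 89%: 395 − 356 = 39 of 71 (55%).
- #2 at 97%: 395 − 388 = 7 of 71 (10%).
- #2 at 97.7%: 395 − 391 = 4 of 71 (6%).

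**The case against.** **The denominator.** Enrolment means signed consent, and the 15% applies to enrolments, while the rule covers only successfully implanted subjects. Consented subjects with no attempt or a failed attempt use up attrition without entering this analysis, and 471 leads is a ceiling. This stands. The all-after-implant figures are one end of a range. It does not rescue #1 unless well over half of the attrition precedes implant.

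**The label.** The tipping-point method is named only as an example, all-failure is one end of any tipping grid, and Section 19 leaves further detail to an SAP that is not shown. A reader might infer that no true tipping-point analysis exists anywhere; the protocol alone cannot support that. The imputation rule, however, is stated without qualification, and an SAP that followed it literally would have nothing to vary.

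**Conservatism.** An all-failure bound is a fair counterweight to a primary cohort that leaves out no-capture cases judged system related, and late visits still count (Section 15.4), which limits missingness. Both are true. They justify keeping the all-failure case, but not having it as the only one.

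**Decision weight.** No criterion hangs on the result. This also stands, and it limits the severity.

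**Conclusion.** The point holds in limited form. As fixed in Section 19.3.2, the sensitivity analysis is a single worst-case imputation. For objective #1 it is driven largely by attrition: the bound is 72.3% if all 15 points follow implant, still 79.3% if 8 of them precede it, and above 80% only from about 9 points (at 90% success) or 10 points (at 89%). These figures rest on 400 evaluable subjects, the plan's expected success rates and assumed splits of the attrition.

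Two stronger conclusions are tempting and not supported. The first is that a trial running to plan would contradict both efficacy conclusions. Objective #2 has an estimate above 80% even in the worst split, misses narrowly on the bound, and passes once a few points of attrition precede implant. The second is that efficacy would be lost. The objectives are judged on the evaluable cohort, and the consequence here is a weak, hard-to-interpret robustness check in the clinical report.

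**What to change.** Replace the fixed rule in Section 19.3.2 with a tipping-point analysis for each efficacy objective:

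- Vary assumed success among non-evaluable implanted subjects from 0% to the observed evaluable rate, and report where the exact one-sided 97.5% lower bound crosses 80%.
- Count lead-attributable cases, such as a deactivated initial lead, as failures throughout this sensitivity analysis, so that only missed visits, exits, deaths and similar cases vary. The required counts above (35 of 71 and 7 of 71) would then have to come from the remaining subjects.
- Keep the all-failure case as the end of the range, and tabulate non-evaluable subjects by reason.
- Optionally, add a version using the 12-month all-vector thresholds for subjects who have them. Deaths, early exits and late enrollees will not, so it can only be supportive.

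The primary analysis need not change. The cost is a revised paragraph and a little more analysis work, with no new data.
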